Smokers are at higher risk of COVID-19 hospitalizations and deaths⁸ and might thus benefit greatly from high vaccination coverage. However, evidence suggests that they may be less likely to be vaccinated, as smokers are less likely to adhere to preventive measures in general and have lower adherence to other vaccines.^{9,10} Reports of a protective role of smoking on the risk of COVID-19 infection might have also reduced the perceived risks from being infected¹¹. Evidence regarding tobacco use and COVID-19 vaccine hesitancy is mixed. Some studies have shown greater mistrust in COVID-19 vaccine benefits¹¹⁻¹⁴ and greater vaccine hesitancy and lower vaccine acceptance compared to non-smokers,^{11,15,16} while other studies have reported no differences by smoking status or lower levels of vaccine hesitancy in smokers compared to non-smokers.¹⁷⁻²⁰

Vaccine uptake, however, is a dynamic process not only influenced by trust and risk perception, but by convenience factors related to physical and geographical availability, affordability, ability to understand and appeal of immunisation services.²¹ To our knowledge, two studies from convenience samples in Singapore and Palestine have examined vaccination uptake by smoking status.^{22,23} Both studies showed that smokers had higher odds of being vaccinated.^{22,23} However, these studies are not representative of the general population and relied on self-reported vaccination status, resulting in a higher risk of selection and information bias. Spacing between vaccine doses is also relevant, as a growing body of literature suggests that smokers develop a weaker immune response to COVID-19 vaccines.²⁴

Finland developed a national COVID-19 vaccination strategy and the vaccine rollout started on December 27, 2020. Vaccinations started with priority groups (health and social care personnel and people at high risk of severe COVID-19) but eventually were expanded to the whole population aged 5 and over.²⁵ COVID-19 vaccines are provided free of charge and delivered nationwide by each municipality. Finland has administered primarily mRNA vaccines (Cominarty and Spikevax).²⁵ Vaccination coverage in the Finnish population aged 18 and older has reached 89.7% for the first dose, 87.6% for the second dose and 65.1% for the booster dose by June 14, 2022.²⁶

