Participants in the FinSote 2020 Survey were adults aged 20 and over derived from the Digital and Population Data Services Registry, created in Jan 2020 after the merge between the Population Register of Statistics Finland and local register offices.²⁹ This sampling frame includes all residents in Finland. The survey was based on a stratified random sample of 22 regions (2000 adults aged 20-74, 800 adults aged 75+, total sample size 61600). Data collection started on September 14, 2020, and finished on February 8, 2021. Participants received a self-administered questionnaire in Finnish, Swedish, English or Russian, which could be returned on paper or filled in electronically. The analytical sample is 28199 participants, with a participation rate of 46%. In 2020, consent to linkage was included in the overall consent, and as a result, we were able to link all participants in the analytical sample.

We will link data from FinSote 2018 and 2020 surveys to the Finnish National Vaccination Register maintained by the Finnish Institute for Health and Welfare using a unique identifier assigned to all residents in Finland. The follow-up will be between December 27, 2020 (date of the first COVID-19 vaccination in the country) until May 31, 2022 or the latest available date.

Outcomes

Our primary outcome will be the vaccination uptake of at least two doses of a COVID-19 vaccine. We will examine four secondary outcomes:

- (i) vaccination uptake of at least one dose of a COVID-19 vaccine,
- (ii) vaccination uptake of the complete COVID-19 vaccination scheme (two doses and a booster dose),
- (iii) proportion of participants with more than 7 months between the first and second COVID-19 dose, and
- (iv) proportion of participants with more than 7 months between second dose and booster dose.

We will include any approved COVID-19 vaccination in Finland by the latest available date (i.e. April 29, 2022):³⁰ COVID-19 mRNA vaccines (Comirnaty and Spikevax), recombinant vaccines (Vaxzevria, COVID-19 vaccine Janssen, COVISHIELD, Nuvaxovid, COVOVAX), and inactivated vaccines (BIBP/Sinopharm, COVAXIN, Coronavac). Participants who have received the COVID-19 vaccine Janssen would be excluded from analyses on the second dose, as the vaccine only requires a single dose.

Exposures

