FinSote surveys 2018 and 2020 are based on a stratified random sample design that represents the Finnish population. However, non-participation in the survey could potentially introduce nonresponse bias if participants are systematically different from non-participants. For this purpose, we will take into account the complex survey design in all analyses and use the inverse probability weights (IPW) created by the Finnish Institute for Health and Welfare using a model with register-based data for the whole sample on age, sex, marital status, educational level, mother tongue and place of residence. The IPW method allows correcting for survey non-participation and the weighting factor of each participant is a combination of the inverse of the participation probability and the sampling probability. Hence, the set of weighted coefficients represents the Finnish population.³⁴

Information bias

The risk of information bias from measurement error of the exposure and confounders is inherent to most population health surveys. However, our data is almost entirely collected before assessment of the outcome, reducing the possibility that the exposure is affected by the occurrence of the outcome (i.e. that COVID-19 vaccination affects tobacco use). COVID-19 vaccination in Finland started on December 27, 2020, with a focus on health and residential care workers. The number of doses available in the first months was limited, so it is unlikely that participants from FinSote 2020 received the vaccination before the data collection. As sensitivity analyses, we will carry out the same analyses but excluding participants who have received a vaccination dose prior to February 8, 2021, when the data collection of FinSote 2020 ended. In addition, smoking status was collected relatively close to the COVID-19 vaccination, reducing (although not excluding it completely) the risk of exposure misclassification.

The COVID-19 vaccination has been implemented nationally by public providers, meaning that all COVID-19 vaccines provided have been registered in the Finnish National Vaccination Register. We estimate the risk of loss to follow-up and information bias of the outcome to be close to zero.

Study size

The sample size was determined by the available data from FinSote surveys 2018 and 2020. We consider it not necessary to provide a sample size calculation.

Quantitative variables

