We described the categorisation of exposures and confounders above. We will model age as a continuous variable and tested non-linearity by comparing the linear model with penalised smoothing splines using a likelihood ratio test.³⁵ The variable years of education will be modelled as categorical to be able to account for secular changes in years of education during the study years. In other words, educational attainment increases over time and it is therefore more appropriate to calculate the educational attainment within each survey wave.

Statistical methods

We will use Poisson regression with robust standard errors to estimate the relative risk of confirmed COVID-19 cases. We will fit the following Poisson model:

$$(1) \quad \log \mu_i = \beta_0 + \beta_1 S_i + \beta_x X_i^* + \rho_1 R_a$$

where i denotes the individual, β_0 is the intercept; β_1 is the coefficient of interest for exposure to tobacco S ; a vector of covariates X^* (i.e., sex, age, marital status, years of education, mother tongue and participation in social activities); and fixed effects $\rho_1 R_a$ for wellbeing area a . We will report the exponentiated coefficient as the relative risk estimate for unadjusted and adjusted models with their corresponding 95% confidence intervals.

We will examine non-linearity between age and the outcome by comparing the linear model with penalised smoothing splines³⁵ using a likelihood ratio test with the Wald method.³⁶ We will use the model with splines if it performs better than the linear model, using a p-value of 0.05 as the threshold for this decision.

We will examine potential effect modification by reporting stratified analyses by age, sex and educational level. If there are noticeable differences, we will test for multiplicative interactions between tobacco use and sex, age and educational level by including an interaction term in equation 1. We will introduce the interaction terms one by one for each of the examined interactions. We will use a likelihood ratio test to compare the model with and without the interaction. A p-value lower than 0.05 in the likelihood ratio test will be used as an indication of the presence of an interaction. If there is evidence of an statistically significant interaction, we will include the interaction term in the final model.

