Our primary method to handle missing data will be multiple imputation, given that a missing at random assumption is the most likely in our data. We will examine patterns of missing data and use multiple imputation using chained equations (MICE). This procedure will be combined with the survey design tools to take the complex sampling design into account.

In sensitivity analyses, we will report estimates using complete case analyses (i.e. taking only the complex sampling design into account). We will also report the same estimates as the main analyses, but restricting the follow-up time to when vaccination coverage reached 60% and 80%. This will allow us to understand whether these associations changed over time and also provide estimates that might be comparable to countries with lower vaccination coverage, thus increasing the external validity of our estimates.

We will analyse the data using R version 4.1.1 and include the statistical code as a Supplementary Appendix.

References

- 2 Davies, N. G. *et al.* Estimated transmissibility and impact of SARS-CoV-2 lineage B.1.1.7 in England. *Science* **372**, eabg3055, doi:doi:10.1126/science.abg3055 (2021).
- 3 Campbell, F. *et al.* Increased transmissibility and global spread of SARS-CoV-2 variants of concern as at June 2021. *Euro Surveill* **26**, doi:10.2807/1560-7917.Es.2021.26.24.2100509 (2021).
- 4 Suthar, A. B. *et al.* Public health impact of covid-19 vaccines in the US: observational study. *BMJ* **377**, e069317, doi:10.1136/bmj-2021-069317 (2022).
- 5 Krause, P. R. *et al.* SARS-CoV-2 Variants and Vaccines. *New England Journal of Medicine* **385**, 179-186, doi:10.1056/NEJMsr2105280 (2021).
- 7 Kuodi, P. *et al.* Association between vaccination status and reported incidence of post-acute COVID-19 symptoms in Israel: a cross-sectional study of patients tested between March 2020 and November 2021. *medRxiv*, 2022.2001.2005.22268800, doi:10.1101/2022.01.05.22268800 (2022).

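### The 60% and 80% coverage snapshots measure how early people were vaccinated in a priority-ordered rollout. They do not support transfer to countries that settled at lower coverage, and they should be limited to one-dose and two-dose uptake.

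*Combined protocol and SAP*

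**What the plan says.** The last part of Statistical methods plans to rerun the main estimates, "restricting the follow-up time to when vaccination coverage reached 60% and 80" per cent. Two purposes are given: to see whether the associations changed over time, and to "provide estimates that might be comparable to countries with lower vaccination coverage, thus increasing the external validity of our estimates". The text does not say which dose or population defines coverage, and it gives no dates for the two thresholds.

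Other parts of the document bear on this:

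- **Background, order of rollout:** "Vaccinations started with priority groups (health and social care personnel and people at high risk of severe COVID-19", with later expansion to the whole population aged 5 and over.
- **Information bias, supply:** "The number of doses available in the first months was limited".
- **Background, adult coverage:** "89.7% for the first dose, 87.6% for the second dose and 65.1% for the booster dose by June 14, 2022".
- **Setting and participants, follow-up:** from December 27, 2020 "until May 31, 2022 or the latest available date"; this is the window for the main analyses.
- **Main and secondary endpoints, listed under Outcomes:** the section opens with the sentence "Our primary outcome will be the vaccination uptake of at least two doses of a COVID-19 vaccine". The secondary outcomes are one dose, two doses plus booster, and two spacing outcomes with a threshold of more than 7 months.
- **Statistical methods, covariates:** "sex, age, marital status, years of education, mother tongue and participation in social activities", plus fixed effects for wellbeing area. Age enters through splines if they fit better than a linear term. No occupation, clinical-risk or eligibility variable is listed.

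**The concern.** A person without the dose when follow-up is cut may not have been offered it, may have been offered it and delayed, or may have refused. The outcome counts all three as non-uptake. In a country whose coverage levelled off at 60% under open access, the unvaccinated are largely people who did not take an available dose. The two situations share a coverage figure but not the reason behind it.

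What is at stake is how the snapshots are read. If the 60% result differs from the main result, a reader could conclude that smokers' acceptance changed over time, or carry the figure over to a lower-coverage country. The difference could instead reflect who stood earlier in the queue. The background section says that smokers have a higher risk of severe COVID-19 and that high-risk people went first, which would move smokers forward. Occupational priority could act in either direction. The sign is therefore not known in advance.

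A second issue is feasibility. Rerunning all the main estimates includes outcomes that need long follow-up or a coverage level that was not reached.

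**Working it through.** The plan gives no expected effect or precision for this analysis, so there is no figure of its own to reproduce. The checks use its coverage figures and add labelled assumptions where it is silent.

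**1. How much non-uptake at the cut is timing?** Let C be coverage at the cut and F the final coverage of the same dose in adults. The share of the unvaccinated at the cut who are vaccinated later is (F − C)/(1 − C).

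| Dose | F | 60% cut | 80% cut |
|---|---|---|---|
| Second | 0.876 | 0.276/0.40 = 69% | 0.076/0.20 = 38% |
| First | 0.897 | 0.297/0.40 = 74% | 0.097/0.20 = 49% (48.5%) |

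These shares include people who were offered a dose and delayed, so they are upper bounds on not yet offered. F is dated June 14, 2022, two weeks after the nominal end of follow-up.

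**2. What can a difference in offer do?** Assume that uptake once offered equals F and does not depend on smoking. The share offered at the cut is then C/F: 0.60/0.876 = 0.685 and 0.80/0.876 = 0.913. The RR at the cut is the share offered in smokers divided by the share offered in never smokers. A 5-point gap remaining after adjustment (an assumption) gives:

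- 60% cut: 0.635/0.685 = 0.93, or 0.735/0.685 = 1.07.
- 80% cut: 0.863/0.913 = 0.945, or 0.963/0.913 = 1.055.

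**3. How much does the planned adjustment remove?** A simulation of 5 × 42,935 people (14,736 + 28,199 = 42,935 linked) set the true uptake RR to 1. Its assumptions, none of which come from the documents, were:

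- age uniform from 20 to 90;
- smoking prevalence 16% below age 65 and 7% from 65;
- rollout from oldest to youngest, with a priority group moved forward by the equivalent of 25 years;
- uptake once offered of 87.6%.

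| Priority share, smokers vs never smokers | Model | RR at 60% | RR at 80% |
|---|---|---|---|
| 20% vs 20% | unadjusted | 0.87 | 0.97 |
| 20% vs 20% | linear age | 1.04 | 1.02 |
| 20% vs 20% | spline age | 0.998 | 1.000 |
| 30% vs 20% | spline age | 1.064 | 1.012 |
| 15% vs 20% | spline age | 0.965 | 0.998 |

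Spline age removes the age-ordered part of the queue. Priority by occupation or clinical risk within age remains, and it is visible mainly at 60%. The plan also reports unadjusted RRs, and those carry the full age-order effect.

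**4. Would such an artefact be noticed as a signal?** Assume 10% of 42,935 exposed (4,294), 20,000 never smokers and a design effect of 2. Then SE(log RR) at 60% is √[2 × (0.4/0.6) × (1/4,294 + 1/20,000)] = 0.019. An RR of 1.064 has log 0.062, about 3 SE from the null. An RR of 0.965 has log −0.036, just under 2 SE.

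**5. Which outcomes fit the snapshots?** The first dose in the country was on December 27, 2020. Adding 7 months gives July 27, 2021, before which no interval above 7 months between first and second dose can exist. The interval from second dose to booster starts later still. A cut soon after that date counts only the few long intervals already completed. Booster coverage was 65.1% on June 14, 2022, so an 80% cut defined on booster coverage is not reached in the planned follow-up.

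**The case against.** The strongest defence has five parts.

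- **The wording is hedged.** The plan claims only possible comparability, and a country still limited by supply could resemble the snapshot. This stands. A reader might infer that the snapshots can never inform another country, but the documents do not support that. The unsupported step is transfer to countries that levelled off under open access.
- **Age and area are adjusted for, and age-stratified results are planned.** This stands for the age-ordered part, provided splines are used. A reader might infer that the whole queue distorts the adjusted RR; only non-age priority does.
- **The residual bias rests on assumed inputs.** This stands. The documents give no priority-group sizes by smoking status, do not describe opening by age group, and state limited supply only for the first months. A single national cut date is the natural reading but is not stated.
- **Uptake in this plan includes availability.** The outcome is receipt of doses, and the background treats availability as part of uptake. So the aim of describing change over time survives, as a description of timing.
- **It is only a sensitivity analysis.** This also stands.

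One tempting figure should not be used. Take acceptance of 90% in never smokers and 85% in smokers, an odds ratio of 0.63. A 60% snapshot caused by supply gives RR 0.85/0.90 = 0.94. A country at 60% through low demand gives 0.486/0.60 = 0.81 with the same odds ratio, or 0.88 with the same hazard ratio. That gap arises because an RR depends on the level of uptake when another measure is held constant. With the RR held at 0.94 and equal offer, both settings give 0.94. It is not evidence of queue bias.

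**Conclusion.** The concern holds in a limited form. The 69% and 38% follow from the plan's own coverage figures, if each cut is defined on second-dose coverage in adults. They show that the 60% snapshot in particular describes earlier against later uptake, so the inference to lower-coverage countries does not follow. A difference between a snapshot and the main result may reflect priority by occupation or clinical risk within age. Under the assumed priority shares, that is an age-adjusted RR of about 1.06 or 0.965 at 60% with no true effect, and within about 1% of 1 at 80%. These sizes illustrate the problem and are not estimates for Finland.

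The limits on the spacing outcomes and the 80% booster cut need no assumption beyond the stated dates and coverage. A reader might infer that the primary result is compromised. It is not, because it uses the full follow-up.

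**What to change.** 1. Restrict the 60% and 80% snapshots to the one-dose and two-dose uptake outcomes. Define each cut as the date on which coverage of that same dose in adults reached the threshold, and state the source and the dates.
2. Replace the external-validity sentence with a statement that the snapshots estimate the association with earlier uptake in a priority-ordered rollout. Do not claim transfer to countries whose coverage levelled off under open access.
3. Optionally, add cuts at each age group's own 60% and 80% coverage as a supplementary analysis, and say that this only partly reduces the priority-group bias. With 30% against 20% priority and no true effect, such cuts moved the simulated RR at 60% from 1.077 to 1.055 in one set-up and from 1.066 to 1.052 in another. That removes 0.022/0.077 = 29% and 0.014/0.066 = 21% of the excess.

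Counting uptake from the date each group became eligible would address the queue more directly, but the plan does not say that eligibility dates are available for linkage.

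The cost is a few sentences of protocol text and, for item 3, some programming with vaccination dates that are already to be linked. The study gives up a favourable, if hedged, claim of external validity.

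### Relative risks of cumulative uptake at 60%, 80% and final coverage cannot by themselves show whether the tobacco association changed over time, and the cut-offs do not suit the booster and spacing outcomes

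*Combined protocol and SAP*

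**What the plan says.** Under Statistical methods, in the paragraph on sensitivity analyses, the main estimates are to be repeated while "restricting the follow-up time to when vaccination coverage reached 60% and 80"%. Two purposes are given. The first is put as "This will allow us to understand whether these associations changed over time". The other is to "provide estimates that might be comparable to countries with lower vaccination coverage". The dose and the population that define coverage are not stated.

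The same section specifies the effect measure: "We will report the exponentiated coefficient as the relative risk estimate for unadjusted and adjusted models with their corresponding 95% confidence intervals". Equation 1 has no time term and no person-time offset. No absolute measure, hazard ratio or test of change across the cut-offs is planned.

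The introduction gives national coverage in adults aged 18 and over as "89.7% for the first dose, 87.6% for the second dose and 65.1% for the booster dose by June 14, 2022". Under Setting and participants, follow-up starts at the rollout on 27 December 2020 and runs "until May 31, 2022 or the latest available date". The outcomes are uptake of at least two doses (primary), at least one dose, two doses plus a booster, and two spacing outcomes defined by more than 7 months between doses.

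**The concern.** The three RRs are cumulative and are taken at very different levels of uptake. If the RR moves as uptake rises while the tobacco effect is steady on another reasonable scale, the reader will see a fading association that is partly or wholly a matter of scale. The three estimates also share the early vaccinations, so they are not independent looks at separate periods. With no second measure and no test, any statement about change would rest on comparing RRs by eye.

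Feasibility is a second issue. The sensitivity analysis is promised for the same estimates as the main analyses, but a coverage cut-off may not exist for the booster outcome, and cutting follow-up early restricts which long intervals can be observed at all.

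The primary result does not depend on this analysis. What is at stake is the conclusion about time trends that the analysis is said to deliver.

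**Working it through.** The plan states no figure for this analysis, so there is none to reproduce.

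**Inputs from the document.** Cut-offs of 60% and 80%; two-dose coverage 87.6%; booster coverage 65.1% on 14 June 2022; planned end of follow-up 31 May 2022; rollout start 27 December 2020.

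**Assumptions, not in the document.** The effect sizes below are illustrative. Never users are set at c = 0.60, 0.80 and 0.876. Strictly, the cut-offs concern overall coverage. Solving instead for overall coverage with 15% exposed gives almost the same result (hazard ratio 0.8: 0.868, 0.908, 0.930).

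**Step 1. Hold one scale constant and compute the RR.**

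- Hazard ratio h: uptake in users = 1 − (1 − c)^h, and RR = that / c.
  - h = 0.8, c = 0.60: 1 − 0.40^0.8 = 0.5196; 0.5196 / 0.60 = 0.866.
  - h = 0.8, c = 0.80: 1 − 0.20^0.8 = 0.7241; 0.7241 / 0.80 = 0.905.
  - h = 0.8, c = 0.876: 1 − 0.124^0.8 = 0.8117; 0.8117 / 0.876 = 0.927.
- Odds ratio θ: uptake in users = θc / (1 − c + θc).
- Constant risk difference of −5 points: RR = (c − 0.05) / c.
- Ceiling model: a share π ever accepts vaccination, with the same timing in both groups, so RR = π₁ / π₀ at every date. With π = 0.85 in users and 0.92 in never users, RR = 0.85 / 0.92 = 0.924.

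| Held constant | RR at 60% | RR at 80% | RR at 87.6% |
|---|---|---|---|
| Hazard ratio 0.8 | 0.866 | 0.905 | 0.927 |
| Hazard ratio 0.7 | 0.789 | 0.845 | 0.877 |
| Odds ratio 0.7 | 0.854 | 0.921 | 0.950 |
| Risk difference −5 points | 0.917 | 0.938 | 0.943 |
| Ceilings 0.85 vs 0.92, same timing | 0.924 | 0.924 | 0.924 |

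**Step 2. Do the alternative measures settle it?** In the hazard ratio 0.8 case the risk differences are −8.0, −7.6 and −6.4 points. In the ceiling case, uptake in users is 0.554, 0.739 and 0.809, giving risk differences of −4.6, −6.1 and −6.7 points. The hazard ratio within each period is the ratio of increments in −log(1 − uptake): 0.88 up to 60%, 0.77 from 60% to 80%, and 0.66 from 80% to 87.6%. So the hazard ratio drifts in the one case where the RR does not. No single scale is neutral, but RR, absolute uptake and risk difference together let a reader tell these patterns apart.

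**Step 3. Booster cut-off.** 80 − 65.1 = 14.9 points short, on a date two weeks after the planned end of follow-up. The 60% level is reached. First and second doses (89.7% and 87.6%) pass both levels.

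**Step 4. Spacing outcomes.** 27 December 2020 plus 7 months is 27 July 2021. Before then no first-to-second interval over 7 months can exist, and second-to-booster intervals over 7 months come later still. For any cut-off date T, a qualifying interval must have begun more than 7 months before T, so an earlier T removes long intervals by construction.

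**The case against.** A reader might infer that the RR is forced toward 1 as coverage rises, so that the analysis is bound to show fading. The documents do not support that. The drift depends on which scale is taken as unchanged, and the plan names none. A ceiling pattern is plausible in a study motivated by hesitancy, and it gives a constant RR. If users also vaccinate faster among the willing (hazard ratio 1.2, same ceilings, 15% exposed), the RR goes 1.018, 0.969, 0.942 and ends farther from 1. The arithmetic cap of 1/c (1.67, 1.25, 1.14) binds only RRs above 1. Below 1, at 87.6% overall coverage, the limit is 0.17, 0.38 or 0.50 for exposed shares of 0.15, 0.20 or 0.25, which is hardly a constraint. This objection stands. It also counts against reading RR movement as change, since neither a moving nor a stable RR identifies what happened.

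A reader might also infer that the aim of comparability with lower-coverage countries fails. It does not: if the RR depends on coverage, that is a reason to report it at lower coverage.

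On feasibility, it would be tempting to say that 80% is never reached for boosters, or that almost no booster or long-interval events precede the 60% date. The plan does not say that cut-offs are dose-specific, and a date set by first- or second-dose coverage would exist. The 65.1% is a national figure for ages 18 and over, whereas the surveys cover ages 20 and over, and follow-up may extend past 31 May 2022. The calendar dates of 60% and 80% coverage are not given, so counts by those dates cannot be stated.

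Finally, this is a descriptive sensitivity analysis with no decision rule. That limits the consequence, but the plan does state what the comparison will show.

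**Conclusion.** The concern holds in a limited form. Comparing cumulative RRs at the two cut-offs and at end of follow-up cannot alone show whether the association changed. Under a constant hazard ratio of 0.8, the apparent deficit shrinks from 13% to 7%; under a constant odds ratio of 0.7 it shrinks from 15% to 5%; with differing ceilings and equal timing it does not move. These sizes rest on assumed effects, and on setting never-user uptake at the cut-offs and at the national two-dose figure.

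On the national 65.1%, a booster-specific 80% cut-off is not reached by the planned end of follow-up. For the spacing outcomes, the 7-month definition makes truncation remove long intervals whatever the exact dates. The primary analysis is unaffected. The change is worth making because it is cheap and alters what this sensitivity analysis can support.

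**What to change.** In the sensitivity-analysis paragraph:

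- Keep the RR, and at each cut-off and at end of follow-up also report adjusted absolute uptake by tobacco group and the risk difference.
- State that movement of the RR across cut-offs will not by itself be read as a change in association. A time-to-dose model with a tobacco-by-period term may be added as supporting analysis, not as the sole basis, since its hazard ratio can drift too (Step 2).
- Define the dose and population behind each cut-off. Apply 60% and 80% to first- and second-dose uptake using that dose's own coverage.
- Do not apply 80% to the booster outcome unless it is reached, and do not apply the cut-offs to the spacing outcomes.
- Leave the lower-coverage-country aim as it is.

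The cost is a few lines of text and more estimates to report. Dose dates are already needed for the spacing outcomes. The optional time-to-dose model costs more than the rest, because it would have to carry the survey weights and multiple imputation for both tobacco exposures.
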